### Time to Progression (TTP)

Time to progression (TTP) is defined as the time from date of the first dose of study treatment to the earliest documented disease progression by Investigator assessment.

TTP will be calculated in months as follows:

$$\text{TTP (months)} = (\text{date of progression or censoring} - \text{date of first dose} + 1)/30.4375$$

TTP will be estimated using the Kaplan-Meier method. The TTP rate at 3, 6, 9, 12, 15 and 18 months will be estimated with corresponding 2-sided 95% CIs.

### Overall Survival (OS)

- Analysis set: Full Analysis Set

OS will be calculated in months as follows:

$$\text{OS (months)} = (\text{date of death or censoring} - \text{date of first dose} + 1)/30.4375$$

OS time will be estimated using the same Kaplan-Meier method. The OS rate at 6, 12, 18, 24, 30 and 36 months will be estimated with corresponding 2-sided 95% CIs.

Frequency (number and percentage) of patients with death events and censoring reasons will be presented by cohort along with the overall event and censor rates. The event and censoring reasons are as follows:

- Death:
  - Death due to COVID-19.
  - Ongoing and no death.
  - Withdrawal of consent.
  - Lost to follow-up.
- The OS time or censoring time and the reasons for censoring will also be presented in a patient listing.

**Phenotypes, and quantity of TIL before and after PF-07260437 treatment (eg, CD3, CD8, Granzyme B, Ki67 IHC)**

### 6.3 Tertiary/Exploratory Endpoint(s)

#### Part 1

##### **Efficacy Analysis**

Response Evaluable Set will be used for ORR and PFS (RECIST, irRECIST). Tumor response will be presented in the form of participant data listings that include, but are not limited to tumor type, tumor response at each visit, and best overall response.

Data will be summarized (also graphically where appropriate) and listed by dose level.

#### Part 1 and 2

##### **Analysis of Pharmacodynamics**

Results of exploratory endpoint analyses will be described in the bSAP and CSR to the extent possible. Due to the exploratory nature of the endpoints, the associated data analyses may not be complete at the time of CSR preparation. If results of exploratory endpoint analyses cannot be included in the CSR, they will be disseminated to the scientific community to the extent possible through presentation at scientific meetings and/or publication in peer-reviewed scientific journals.

### 6.5 Baseline and Other Summaries and Analyses

#### 6.5.1 Baseline Summaries

Baseline characteristics such as demographics, prior medication, and primary diagnosis will be tabulated and listed. The Safety Analysis Set will be used.

#### 6.5.2 Study Conduct and Participant Disposition

An accounting of the study participants will be tabulated. The participant dose level cohort will be listed. The Full Analysis Set will be used.

Participant discontinuation from treatment and study will be tabulated and listed for each participant separately with their reason for discontinuation. The Safety Analysis Set will be used.

### 6.5.3 Study Treatment Exposure

The Safety Analysis Set will be used.

Dose modifications are described in the protocol. The following will be summarized by treatment dose level and overall:

- Number of subjects;
- Median and range of number of treatment cycles started;
- Number (%) of subjects starting a treatment cycle (1, 2, 3...);
- Number (%) of dose interruptions (include both known and unknown dates). Dose interruptions is defined as as a planned dosing day with 0 mg total dose administered. Missing doses on unknown dates will be included in the summary. Note: Dose interruptions apply to unexpected dose interruptions and not the one-week treatment holiday given in each treatment cycle;
- Number (%) of dose interruptions related to AEs, defined as “Was the Actual Dose adjusted from planned?” = “ADVERSE EVENT(S)” and “Latest Action Taken with Study Treatment:” = “DOSE INTERRUPTED”;
- Number (%) of subjects with dose reductions. A dose reduction is defined as a day when the actual dose is less than the planned dose at enrollment and the acutal dose is greater than 0 mg (i.e., missed doses are not counted as a reduction);
- Number (%) of dose reductions related to AEs, defined as “Was the Actual Dose adjusted from planned?” = “ADVERSE EVENT(S)” and “Latest Action Taken with Study Treatment:” = “DOSE REDUCED”;
- Number (%) of participants with dose reductions or interruptions for each reason (AE vs insufficient clinical response vs Other);
- Days on treatment (median, range).
- Number of treatment cycles received per subject (median, range);
- Number of treatment cycles received before 1st reduction (median, range);
- Number of treatment cycles received before 1st interruption (median, range).

The following will be summarized for cumulative dose by dose level:

- Summary statistics (mean, median, standard deviation and range) of cumulative dose and cumulative percent of administered dose (compared to planned dose);
- Actual dose intensity (mg/day): Defined as cumulative actual dose received (mg) divided by the number of doses scheduled per protocol during treatment period;
- Ratio of actual dose intensity to planned dose intensity. Where planned dose intensity is defined as a participant's planned starting dose.

Listings by subject (ordered by dose level): start date and stop date of dosing period within each cycle (including records with 0 mg), total daily dose received for each dosing period, any missed doses with unknown dates (yes/no), number of missed doses with unknown dates, reason for any dosing changes, and cycle number relative to the dosing period.

Listings by subject and cycle (ordered by dose level): cycle length, total planned dose, total actual dose received, percentage of planned dose, dose reduction (yes/no), and dose interruption (yes/no).

#### 6.5.4 Concomitant Medications and Nondrug Treatments

Prior, concomitant, and further therapies (drug and non-drug treatments) will be coded by the World Health Organization (WHO) medical dictionary. Listings of prior, concomitant, and further therapies will be provided separately.

#### 6.6 Safety Summaries and Analyses

All safety analyses will be performed on the Safety Analysis Set.

Summaries and analyses of safety parameters will include all participants in the safety analysis set.

AEs, ECGs, blood pressure (BP), pulse rate, ophthalmic examinations and safety laboratory data will be reviewed and summarized on an ongoing basis during the study to evaluate the safety of participants. Any clinical laboratory, ECG, BP, and pulse rate abnormalities of potential clinical concern will be described. Safety data will be presented in tabular and/or graphical format and summarized descriptively, where appropriate.

Medical history and physical examination and neurological examination information, as applicable, collected during the course of the study will be considered source data and will not be required to be reported, unless otherwise noted. However, any untoward findings identified on physical/or neurological examinations examinations conducted during the active collection period will be captured as AEs, if those findings meet the definition of an AE. Data collected at screening that are used for inclusion/exclusion criteria, such as laboratory data, ECGs, and vital signs, will be considered source data, and will not be required to be reported, unless otherwise noted. Demographic data collected at screening will be reported.

### 6.6.1 Adverse Events

AEs will be graded by the investigator according to the CTCAE version 5.0 and coded using the Medical Dictionary for Regulatory Activities (MedDRA, version 23.1). Adverse event data will be reported in tables and listings. Summaries of adverse event by system organ class and preferred terms, toxicity grade, and seriousness and relationship to study treatment will be presented, as well as summaries of adverse events leading to death and premature withdrawal from study treatment. The number and percentage of participants who experienced any AE, SAE, treatment related AE, and treatment related SAE will be summarized according to worst toxicity grades. The summaries will present AEs across the entire study period. A table summarizing whether deaths were on (i.e., death  $\leq$  30 Days From Last Dose of Study Treatment) or off study treatment (i.e., death  $>$  30 Days From Last Dose of Study Treatment) will be provided. Additionally, listings of DLTs and deaths will be provided. Death and SAE information will be based on the data captured from the CRF.

A similar approach will be used for irAEs.

### 6.6.2 Clinical Safety Laboratory Assessments

Safety laboratory tests will be performed as described in the protocol.

To determine if there are any clinically significant laboratory abnormalities, the hematological, clinical chemistry and urinalysis safety tests will be assessed against the criteria specified in the sponsor reporting standards. The assessment will take into account whether each subject's baseline test result is within or outside the laboratory reference range for the particular laboratory parameter.

The data may be summarized with respect to demographic and baseline characteristics, efficacy observations and measurements, safety observations and measurements, pharmacokinetic and biomarker measurements.

### 6.6.3 Vital Signs

Vital signs will consist of systolic and diastolic blood pressure, and pulse rate measurements. Criteria for clinically relevant abnormal findings are provided in [Appendix 2. Measurements](#) that meet these criteria will be listed.

### 6.6.4 Electrocardiograms

The analysis of ECG results will be based on participants in the Safety Analysis Set with baseline and on-treatment ECG data. Baseline is defined as measurements taken at Cycle 1 Day 1 pre-dose (see [SoA in protocol](#) for details).

Changes from baseline for the ECG parameters QT interval, heart rate, QTc interval, pulse rate interval, and QRS complex will be summarized by treatment and time.

The number (%) of participants with maximum postdose QTcF values and maximum increases from baseline in the following categories will be tabulated by treatment cohort:

### Safety QTcF Assessment

Degree of Prolongation	Mild (msec)	Moderate (msec)	Severe (msec)
Absolute value	>450-480	>480-500	>500
Increase from baseline	NA	30-60	>60

In addition, the number of participants with QTcF values >500 msec will be summarized.

Electrocardiogram (ECG) measurements (an average of the triplicate measurements) will be used for the statistical analysis and all data presentations.

If more than 1 ECG is collected at a nominal time after dose administration (for example, triplicate ECGs), the mean of the replicate measurements will be used to represent a single observation at that time point. If any of the 3 individual ECG tracings has a QTcF value >500 msec, but the mean of the triplicates is not >500 msec, the data from the participant's individual tracing will be described in a safety section of the CSR in order to place the >500-msec value in appropriate clinical context. However, values from individual tracings within triplicate measurements that are >500 msec will not be included in the categorical analysis unless the average from the triplicate measurements is also >500 msec. Changes from baseline will be defined as the change between the postdose QTcF value and the average of the predose triplicate values on Day 1.

In addition, an attempt will be made to explore and characterize the relationship between plasma concentration and QT interval length using a PK/pharmacodynamic modeling approach. If a PK/pharmacodynamic relationship is found, the impact of participant factors (covariates) on the relationship will be examined.

The analysis of ECG results will be based on participants in the Safety Analysis Set with baseline and on-treatment ECG data.

ECG measurements (an average of the triplicate measurements) will be used for the statistical analysis and all data presentations. Any data obtained from ECGs repeated for safety reasons after the nominal time-points will not be averaged along with the preceding triplicates. Interval measurements from repeated ECGs will be included in the outlier analysis (categorical analysis) as individual values obtained at unscheduled time points.

QT intervals will be corrected for heart rate (HR) (QTc) using the standard correction factor of Fridericia. Data will be summarized and listed for QT, HR, RR, pulse rate, QRS, QTcF, time and dose. Descriptive statistics (n, mean, median, standard deviation, minimum, and maximum) will be used to summarize the absolute corrected QT interval and changes from baseline in corrected QT after treatment, by dose and time point.

#### 6.6.5 Physical Examination

Participants will have a physical examination to include weight, vital signs, assessment of ECOG performance status and height; height will be measured at baseline only.

## 7. INTERIM ANALYSES

No formal interim analysis will be conducted for this study. As this is an open-label study, the sponsor may conduct unblinded reviews of the data during the study for the purpose of safety assessment, facilitating dose-escalation decisions, facilitating PKmodeling, and/or supporting clinical development.

## 9. APPENDICES

### Appendix 1 Time to Event Data Analysis Censoring Rules

**Table 4 OS Outcome and Event Dates**

Situation	Date of Death/Censoring	Outcome
Alive	Date of Last Contact	Censored
Death due to any cause	Date of Death	Event

### Appendix 2 Categorical Classes for ECG and Vital Signs

#### Clinically Relevant Categories for QTcF

QTcF (msec)	max. $\leq$ 450	450 $<$ max. $\leq$ 480	480 $<$ max. $\leq$ 500	max. $>$ 500
QTcF (msec) increase from baseline	30 $\leq$ max. $<$ 60	max. $\geq$ 60		

#### Clinically Relevant Categories for Pulse Rate and QRS

Pulse Rate (msec)	max. $\geq 300$	
Pulse Rate (msec) increase from baseline	Baseline $>200$ and max. $\geq 25\%$ increase	Baseline $\leq 200$ and max. $\geq 50\%$ increase
QRS (msec)	max. $\geq 200$	
QRS (msec) increase from baseline	Baseline $>100$ and max. $\geq 25\%$ increase	Baseline $\leq 100$ and max. $\geq 50\%$ increase

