8.2.3. Electrocardiograms

A single 12-lead ECG will be utilized as screening. A triplicate 12-lead ECGs will be utilized for Cycles 1 to 3 to determine mean QTcF interval. For the days of dose administration, perform ECG up to 60 minutes prior to dosing (SC or IV), and at the end of infusion (IV only).

From Cycle 4 onwards: Triplicate 12-lead ECG up to 60 minutes prior to dosing on Day 1 of every 3 cycles (C4D1, C7D1, etc.).

Standard 12-lead ECGs utilizing limb leads (with a 10 second rhythm strip) should be collected at times specified in the [SOA](#) section of this protocol using an ECG machine that automatically calculates the heart rate and measures PR, QT, and QTc intervals and QRS complex. Alternative lead placement methodology using torso leads (eg, Mason-Likar) should not be used given the potential risk of discrepancies with ECGs acquired using standard limb lead placement. All scheduled ECGs should be performed after the participant has rested quietly for at least 5 minutes in a supine position.

To ensure safety of the participants, a qualified individual at the investigator site will make comparisons to baseline measurements. Additional ECG monitoring will occur if a) the mean value from the triplicate measurements for any postdose QTcF interval is increased by ≥ 60 msec from the baseline and is > 450 msec; or b) an absolute QTcF value is ≥ 500 msec for any scheduled ECG. If either of these conditions occurs, then a single ECG measurement must be repeated at least hourly until QTcF values from 2 successive ECGs fall below the threshold value that triggered the repeat measurement. In addition, if verified QTcF values continue to exceed the criteria above, immediate correction for reversible causes including electrolyte abnormalities, hypoxia, and concomitant medications for drugs with the potential to prolong the QTcF interval should be performed.

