9.3.5.1. Electrocardiogram Analyses

Changes from baseline for the ECG parameters QT interval, heart rate, QTcF, PR interval, and QRS complex will be summarized by treatment and time.

The number (%) of participants with maximum postdose QTcF values and maximum increases from baseline in the following categories will be tabulated by treatment:

Safety QTcF Assessment

Degree of Prolongation	Mild (ms)	Moderate (ms)	Severe (ms)
Absolute value	>450-480	>480-500	>500
Increase from baseline		30-60	>60

If more than 1 ECG is collected at a nominal time after dose administration (for example, triplicate ECGs), the mean of the replicate measurements will be used to represent a single observation at that time point. If any of the 3 individual ECG tracings has a QTcF value >500 ms, but the mean of the triplicates is not >500 ms, the data from the participant's individual tracing will be described in a safety section of the CSR in order to place the >500 ms value in appropriate clinical context. However, values from individual tracings within triplicate measurements that are >500 ms will not be included in the categorical analysis unless the average from the triplicate measurements is also >500 ms. Changes from baseline will be defined as the change between the postdose QTcF value and the average of the time-matched baseline triplicate values on Day -1, or the average of the predose triplicate values on Day 1.

In addition, an attempt will be made to explore and characterize the relationship between plasma concentration and QT interval length using a PK/pharmacodynamics modeling approach. If a PK/pharmacodynamics relationship is found, the impact of participant factors (covariates) on the relationship will be examined.

The analysis of ECG results will be based on participants in the safety analysis set with baseline (pre-dose on Cycle 1 Day 1) and on-treatment ECG data.

ECG measurements (an average of the triplicate measurements) will be used for the statistical analysis and all data presentations. Any data obtained from ECGs repeated for safety reasons after the nominal time points will not be averaged along with the preceding triplicates. Interval measurements from repeated ECGs will be included in the outlier analysis (categorical analysis) as individual values obtained at unscheduled time points.

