QT intervals will be corrected for HR using standard correction factors (ie, Fridericia's (default correction), Bazett's, and possibly a study-specific factor, as appropriate). Data will be summarized and listed for QT, HR, RR, PR, QRS, QTcF (and other correction factors, eg, QTcB as appropriate), and by study treatment (ie, monotherapy versus combination therapy) and dose. Individual QT (all evaluated corrections) intervals will be listed by study treatment, time, and dose. The most appropriate correction factor will be selected and used for the following analyses of central tendency and outliers and used for the study conclusions. Descriptive statistics (n, mean, median, standard deviation, minimum, and maximum) will be used to summarize the absolute corrected QT interval and changes from baseline in corrected QT after treatment by study treatment, dose, and time point. Details of additional analysis (if any) will be specified in SAP.

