10.7. Appendix 7: ECG Findings of Potential Clinical Concern

ECG Findings That May Qualify as AE

Marked sinus bradycardia (rate <40 bpm) lasting minutes.New PR interval prolongation >280 ms.New prolongation of QTcF to >480 ms (absolute) or by \geq60 ms from baseline.New-onset atrial flutter or fibrillation, with controlled ventricular response rate: ie, rate <120 bpm.New-onset type I second-degree (Wenckebach) AV block of >30 seconds' duration.Frequent PVCs, triplets, or short intervals (<30 seconds) of consecutive ventricular complexes.
ECG Findings That May Qualify as Serious AE

QTcF prolongation >500 ms.New ST-T changes suggestive of myocardial ischemia.New-onset left bundle branch block (QRS >120 ms).New-onset right bundle branch block (QRS >120 ms).Symptomatic bradycardia.Asystole:
In awake, symptom-free participants in sinus rhythm, with documented periods of asystole \geq3.0 seconds or any escape rate <40 bpm, or with an escape rhythm that is below the AV node.In awake, symptom-free participants with atrial fibrillation and bradycardia with 1 or more pauses of at least 5 seconds or longer.Atrial flutter or fibrillation, with rapid ventricular response rate: rapid = rate >120 bpm.Sustained supraventricular tachycardia (rate >120 bpm) ("sustained" = short duration with relevant symptoms or lasting >1 minute).Ventricular rhythms >30 seconds' duration, including idioventricular rhythm (heart rate <40 bpm), accelerated idioventricular rhythm (HR >40 bpm to <100 bpm), and

monomorphic/polymorphic ventricular tachycardia (HR >100 bpm (such as torsades de pointes)).

- Type II second-degree (Mobitz II) AV block.
- Complete (third-degree) heart block.

ECG Findings That Qualify as SAE

- Change in pattern suggestive of new myocardial infarction.
- Sustained ventricular tachyarrhythmias (>30 seconds' duration).
- Second- or third-degree AV block requiring pacemaker placement.
- Asystolic pauses requiring pacemaker placement.
- Atrial flutter or fibrillation with rapid ventricular response requiring cardioversion.
- Ventricular fibrillation/flutter.
- At the discretion of the investigator, any arrhythmia classified as an adverse experience.

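### The SAP's ECG sections name pulse rate where the protocol names the PR interval, so the PR-interval summaries and listings the protocol requires are not specified

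*SAP*

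**What the plan says.** Protocol Section 9.3.5.1 names five parameters for change from baseline: "Changes from baseline for the ECG parameters QT interval, heart rate, QTcF, PR interval, and QRS complex". Later in the same section it sets the wider reporting: "Data will be summarized and listed for QT, HR, RR, PR, QRS, QTcF". The interval is collected. Protocol Section 8.2.3 calls for a machine that "automatically calculates the heart rate and measures PR, QT, and QTc intervals and QRS complex". Protocol Appendix 7 lists "New PR interval prolongation >280 ms" among ECG findings that may qualify as an adverse event.

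The SAP departs from this in three places.

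- **Section 6.6.4, change-from-baseline sentence:** "ECG parameters QT interval, heart rate, QTc interval, pulse rate interval, and QRS complex will be summarized".
- **Section 6.6.4, closing paragraph:** the summary and listing sentence has pulse rate between RR and QRS, where the protocol has PR.
- **Appendix 2, ECG categories:** the heading pairs pulse rate with QRS. One row sets an absolute criterion for pulse rate in msec (maximum of 300 or more). The next, "Pulse Rate (msec) increase from baseline", sets a 25% or 50% increase according to whether baseline is above 200.

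The next table in Appendix 2 has a separate vital-signs row for supine pulse rate in bpm, with limits of 40 and 120.

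**The concern.** A SAP is the text from which outputs are specified. Here the operative sentences carry the wrong parameter name, so the protocol's PR-interval summaries and listings have no counterpart in the SAP. The PR interval is not named anywhere else in it, and its abbreviation list gives PR only as partial response.

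At stake is a planned safety display in a first-in-human study that uses no data monitoring committee. A programmer following the text would either produce a second heart-rate summary under another name or have to guess what was meant. The Appendix 2 criteria would be equally unclear.

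**Working it through.** There is no sample-size or error-rate figure to reproduce. The check is a comparison of texts and one conversion of units.

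**Step 1: parallel sentences.**

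| Element | Protocol 9.3.5.1 | SAP 6.6.4 |
|---|---|---|
| Change from baseline | QT, heart rate, QTcF, PR interval, QRS | QT, heart rate, QTc, pulse rate interval, QRS |
| Summarised and listed | QT, HR, RR, PR, QRS, QTcF | QT, HR, RR, pulse rate, QRS, QTcF |

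In each line pulse rate sits exactly where PR stood. Heart rate is already present in both, so pulse rate adds nothing, and a pulse rate interval is not defined in either document. One of five parameters is displaced in the first line and one of six in the second.

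**Step 2: can the Appendix 2 cut-offs apply to pulse rate?** Inputs are the msec unit and the values 300 and 200 from that table. The conversion is beat-to-beat interval in msec = 60000 / rate in bpm.

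- Ignore the unit and read bpm: a maximum of 300 or more would in practice never be met.
- Keep msec and read it as a beat-to-beat interval: 60000 / 300 = 200 bpm, so everyone with a rate of 200 bpm or less meets the criterion.
- On the same scale, a baseline of 200 msec or less means 60000 / 200 = 300 bpm or more.

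Neither reading gives a usable category. The unit and the pairing with QRS fit an ECG interval, and the protocol sentences name which one.

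**Step 3: likely origin.** The protocol's abbreviation list expands PR as partial response, progesterone receptor or pulse rate, and omits the ECG interval. In the general safety paragraph (protocol 9.3.5, SAP 6.6), PR next to blood pressure became pulse rate, and correctly so. The same expansion in the ECG text is wrong.

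**Step 4: is it deliberate?** Protocol Section 9 lets the SAP modify the plan. The SAP states no intention to drop the PR interval, and its introduction says it adds detail to the analyses outlined in the protocol.

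**The case against.** The strongest reply is that this is a labelling slip that gives itself away. The msec unit, the undefined pulse rate interval and the separate bpm row should each alert a careful programmer, and the protocol's own requirement was never withdrawn. That is fair. It lowers the chance of harm but does not supply the missing specification.

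Several stronger inferences should be resisted.

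- **That PR prolongation would go unseen.** Protocol Section 7.1.1 asks for any new clinically relevant ECG finding to be reported as an adverse event. Appendix 7 describes its findings as alerts from the core ECG laboratory to the investigator and study team. SAP Section 6.6 says ECG abnormalities of potential clinical concern will be described. None of these depends on the mislabelled text.
- **That the protocol requires categorical PR analysis.** Its statistical section requires PR summaries and listings, and the only ECG categories it tabulates are for QTcF. The PR-type cut-offs exist only in the SAP.
- **That an outlier table is lost.** SAP 6.6.4 tabulates QTcF categories only and does not refer to Appendix 2. The note closing the Appendix 2 tables says qualifying measurements are to be listed.
- **That no participant could meet the 300 criterion.** This holds only if the stated unit is ignored. Taken in msec as a beat-to-beat interval, nearly everyone would meet it.
- **That correcting the label would reproduce the Appendix 7 finding.** The SAP's absolute criterion is 300 or more, while Appendix 7 uses above 280.

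**Conclusion.** The point holds as a wrong parameter name in operative analysis text, at three places in the SAP. As written, the SAP omits the PR-interval change-from-baseline summaries and the PR summaries and listings in protocol 9.3.5.1, and its Appendix 2 msec criteria are attached to a rate.

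The size is small: one of the five ECG parameters in the change-from-baseline sentence, with the data still collected and other routes to reporting intact. No dose-limiting toxicity, dose-escalation or efficacy analysis is affected.

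The practical consequence assumes that the SAP is followed literally. That PR interval was intended is an inference from the matching sentences, the unit and the cut-offs. The documents do not say so outright, but no other reading makes the text coherent.

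**What to change.** In SAP Section 6.6.4, write PR interval in place of pulse rate interval in the change-from-baseline sentence, and in place of pulse rate in the summary and listing sentence. In the Appendix 2 ECG categories, make the same replacement in the heading and in both msec rows. Add PR interval to the SAP abbreviations, distinct from partial response. Leave the vital-signs row for pulse rate in bpm, and the pulse rate references in SAP Sections 6.6 and 6.6.3, unchanged.

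The cost is a word replacement in the SAP, best made before the ECG outputs are programmed. It needs no change to design, data collection or sample size.
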